5.5.1.3 Potential Toxicity of Liposomal Curcumin Administered with Temozolomide

This study will investigate the safety and tolerability of LC when co-administered with the alkylating agent TMZ as routinely administered during standard of care CRT and adjuvant chemotherapy regimens in the treatment of newly diagnosed HGG. Currently, there is no human safety study to suggest that there are any risks or benefits to this combination. However, interferences with cytotoxic drugs such as irinotecan, mechlorethamine, doxorubicin, and cyclophosphamide, as well as synergistic effects with 5-fluorouracil may occur. Enhancement or exaggeration of *Ginkgo biloba* effects,

hypoglycemia with diabetes medications, and lipid lowering with cholesterol-lowering drugs may also be observed. Appropriate monitoring of blood sugar and cholesterol parameters should be performed in patients with these comorbid conditions.

CYP450 studies have been conducted and show no tendency for inhibition or induction of the common CYP450 drug metabolism enzymes. It is therefore not expected that LC will have any major drug-drug interactions. No specific restrictions with respect to other drugs metabolized via CYP450 enzymes is necessary.

5.5.1.4 *Liposomal Curcumin Dosing Precautions*

Because of the potential for allergenic reactions with liposomal drug delivery vehicles, patients will be pre-dosed with 4 mg IV dexamethasone and 25 mg diphenhydramine prior to each infusion. Patients who are already on maintenance dexamethasone of at least 4 mg daily can defer the additional IV premedication of dexamethasone if this medication has been orally administered on the morning prior to their infusions.

Recommended dose adjustments based on symptoms are described in [Section 5.10](#).

5.5.2 *Temozolomide*

5.5.2.1 *General Information*

Generic name: Temozolomide

Commercial name: Temodar[®]

IUPAC name: 3,4-dihydro-3-methyl-4-oxoimidazo[5,1-d]-tetrazine-8 carboxamide

Classification: Antineoplastic agent, alkylating

Molecular formula: C₆H₆N₆O₂

Molecular weight: 194.15

Appearance: White to light tan/light pink powder

Melting point: Decomposes at 206°C

How supplied: Commercially available

5.5.2.2 *Mechanism of Action*

Temozolomide is not directly active but undergoes rapid non-enzymatic conversion at physiologic pH to the reactive compound 5-(3-methyltriazen-1-yl)-imidazole-4-carboxamide (MTIC). The cytotoxicity of MTIC is thought to be primarily due to alkylation of DNA. Alkylation (methylation) occurs mainly at the O₆ and N₇ positions of guanine.

5.5.2.3 *Stability*

The molecule is stable at acidic pH (< 5), and labile at pH > 7, hence TMZ can be administered orally. The prodrug, TMZ, is rapidly hydrolyzed to the active MTIC at

neutral and alkaline pH values, with hydrolysis taking place even faster at alkaline pH. The product label recommends storage at 25°C (77°F); excursions permitted to 15°C to 30°C (59°F to 86°F).

5.5.2.4 *Half-life*

Temozolomide is rapidly eliminated with a mean elimination half-life of 1.8 hr.

5.5.2.5 *Packaging, Dispensing, and Storage*

TEMODAR capsules are available in strengths of 5, 20, 100, 140, 180, and 250 mg. The capsules contain a white capsule body with a color cap and the colors vary based on the dosage strength. The 5-mg, 20-mg, 100-mg, 140-mg, and 180-mg capsule strengths are available in 5-count and 14-count packages. The 250-mg capsule strength is available in a 5-count package. Labeling of the packages containing the capsules will be done in accordance with the local procedures (as required by law). The hospital pharmacist will deliver the TMZ dosage for a complete cycle to the patient.

5.5.2.6 *Known Potential Toxicities of Temozolomide*

Known potential toxicities of TMZ are hematological toxicities (leucopenia, lymphopenia, thrombocytopenia, and anemia), renal insufficiency, nausea and vomiting, liver enzyme abnormalities, lethargy, rash, headache, alopecia, constipation, fatigue/malaise, anorexia, hyperglycemia, and diarrhea. Recently, cases of hepatic injury, including fatal hepatic failure, have been observed in patients enrolled in clinical studies utilizing TMZ. In addition, it was noted that liver toxicity may occur several weeks or more after initiation of treatment or after TMZ discontinuation. Refer to the package insert for additional information on AEs observed to date ([TEMODAR package insert, 2019](#)).

Rats given TMZ in recent multidose toxicity studies have developed adenocarcinoma of the breast, fibrosarcomas, malignant schwannomas (a variant of fibrosarcoma), keratoacanthomas, and basal cell adenomas. Similar studies conducted in dogs did not reveal any similar findings. The significance of this finding for humans is not known presently.

If liver function tests (alkaline phosphatase, total bilirubin, SGOT, SGPT) are abnormal, the decision to initiate TMZ treatment should carefully consider the benefits and risks for the individual patient. For patients with significant liver function abnormalities, the benefits and risks of continuing treatment should be carefully considered.

Temozolomide is potentially mutagenic and should be handled with appropriate precautions by both staff and patients. Patients with known or suspected hypersensitivity to TMZ should not be treated with TMZ. There are no data available on the effect or management of TMZ overdose. Additional information is available in the TMZ package insert ([TEMODAR package insert, 2019](#)).

5.5.3 *Temozolomide Dosing Precautions*

Nausea Prevention/Treatment: Patients will be instructed to administer TMZ at night before bedtime on an empty stomach. Patients will be prescribed ondansetron at 8 mg to administer 30 minutes prior to chemotherapy ingestion as well as every 8 hr as needed. Patients can additionally be prescribed prochlorperazine at 5-10 mg as needed every 6 hr per Investigator preference.

Constipation Prevention/Treatment: Patients may be prescribed polyethylene glycol 3350 (eg, MiraLAX[®]) 16 g daily as needed, docusate (50-100 mg every 6 hr as needed), or senna glycoside (20 mg every 12 hr as needed) per Investigator preference.

Recommended dose adjustments based on symptoms are described in [Section 5.10](#).

For patients receiving concurrent TMZ and LC, blood counts will be evaluated weekly. Within -5 days (5 days prior to) the first dose of each 5-day TMZ treatment, the patient must have an ANC $\geq 1500/\mu\text{L}$ and platelet count $\geq 100,000/\mu\text{L}$. On Day 1 of each cycle (within -5 days) all nonhematological Grade 3 or 4 toxicities (except for alopecia, nausea and vomiting, and lymphopenia), that is definitely, probably, or possibly related to TMZ must have resolved (Common Terminology Criteria for Adverse Events [CTCAE] Grade ≤ 1). If toxicity persists, treatment should be delayed by 1 week for up to 3 consecutive weeks. If after 3 weeks of delay all toxicity has still not resolved, any further adjuvant treatment with TMZ should be stopped.

5.5.4 *Radiotherapy*

No specific prophylaxis is indicated for the RT regimen. The Investigator may use low-dose benzodiazepines if clinically indicated for anxiolytic management if compliance is an issue.

Modalities: Only conformal techniques (3-dimensional conformal radiotherapy [3D CRT] or intensity-modulated radiotherapy [IMRT]) will be allowed in this study. Proton radiotherapy is not allowed. Two-dimensional techniques not employing volumetric target volume definition or 3-dimensional assessments of radiation dose are not allowed. The radiation technology utilized as well as the dosing and target volumes are determined according to current standard of care and described below. In most circumstances IMRT will be optimal as most target volumes are convex or concave, such that there would likely be an advantage in protection of critical structures and brain.

Equipment: All patients must be treated with a linear accelerator with nominal photon energy between 6 to 18 MV. Co-60 is not allowed on this study. Electrons and protons may not be used.

Additional information on treatment planning may be found in [Section 9.2](#) (Appendix 2).

5.5.4.1 *Potential Toxicity of Radiotherapy*

Side effects of radiation may occur in an increased frequency and severity when receiving LC along with standard RT and TMZ.

The following side effects may be associated with RT for brain cancer:

Likely:

- Tiredness including mental slowing
- Lack of energy
- Redness or soreness of scalp
- Hair loss (temporary or permanent)
- Short-term hearing loss
- Possible increase in brain tumor symptoms such as headaches, seizures, or weakness during treatment
- Edema or swelling of the brain that may require steroid medication

Less Likely:

- Nausea
- Vomiting
- Permanent mental slowing
- Permanent hearing loss
- Cataracts
- Behavioral change
- Temporary worsening of existing neurological deficits, such as decreased vision, drowsiness
- Changes in the level of some hormones related to changes to the pituitary gland
- Dry mouth or altered taste

Uncommon but Serious:

- Severe local damage to normal brain tissue, a condition called necrosis (tissue deterioration). Radiation necrosis can mimic recurrent brain tumor and may require surgery for diagnosis and treatment.
- Injury to brain causing permanent neurologic deficits or disability
- Injury to brain causing severe cognitive slowing
- Injury to the eyes with the possibility of blindness

Rare

- Development of other tumors (either benign or malignant)

5.6 Preparation/Handling/Storage/Accountability

1. The Investigator or designee must confirm appropriate temperature conditions for study interventions have been maintained during transit for all study intervention

received and any discrepancies are reported and resolved before use of the study intervention.

2. Only patients enrolled in the study may receive study intervention and only authorized site staff may supply or administer study intervention. All study intervention must be stored in a secure, environmentally controlled, and monitored (manual or automated) area in accordance with the labeled storage conditions with access limited to the Investigator and authorized site staff.
3. The Investigator, institution, or the head of the medical institution (where applicable) is responsible for study intervention accountability, reconciliation, and record maintenance (ie, receipt, reconciliation, and final disposition records).
4. Further guidance and information for the final disposition of unused study interventions are provided in the Laboratory Manual.

5.7 Measures to Minimize Bias: Randomization and Blinding

This is an open-label study that is not controlled, randomized, or blinded. Patients with be assigned to a dose level of LC at study entry, based on order of entry and decisions made by the SRC using the TITE-BOIN design described in [Section 8](#).

5.8 Study Intervention Compliance

Patient compliance with TMZ will be assessed at each visit following the weeks during which TMZ is administered in the CRT and adjuvant periods. Compliance will be assessed by direct questioning and by counting returned capsules. Deviations from the prescribed dosage regimen should be recorded in the CRF.

5.9 Concomitant Therapy

Prohibited concomitant therapies are listed in [Section 5.9.1](#). Other than these agents, no specifically known drug interactions will exclude patients from enrollment. In early studies, curcumin has been shown to exaggerate effects from *Ginkgo* spp., hypoglycemic agents, and cholesterol-lowering agents, and patients should be monitored for these metabolic effects or encouraged to reduce or eliminate these medications from their regimen. According to in vitro studies, there is no to minimal inhibition or induction of the common CYP450 drug metabolism enzymes. As part of the enrollment/informed consent procedures, the patient will be counseled on the risk of interactions with other agents, and what to do if new medications need to be prescribed or if the patient is considering a new over-the-counter medicine or herbal product.

Any medication or vaccine (including over-the-counter or prescription medicines, vitamins, and/or herbal supplements) that the patient is receiving at the time of enrollment or receives during the study must be recorded along with:

- Reason for use
- Dates of administration including start and end dates
- Dosage information including dose and frequency

The Medical Monitor should be contacted if there are any questions regarding concomitant or prior therapy.

Patients must abstain from taking curcumin supplements during the study.

5.9.1 Prohibited Therapies

No investigational or commercial agents or therapies may be used during the study to treat the patient's malignancy other than those specified by this protocol.

In addition, the following commonly-used drugs and drug classes are not permitted during the study:

- Levofloxacin
- Penicillins
- Cephalosporins
- Ibuprofen (patients should also be instructed not to take this medication at home)
- Methyldopa
- Quinidine

5.9.2 Rescue Medicine

Patients who exhibit possible infusion reactions despite premedication should be discussed with the Medical Monitor.

5.10 Dose Modification

This protocol allows some alteration from the currently outlined dosing schedule, but the maximum dose of LC will not exceed 400 mg/m².

The decision to proceed to the next dose level of (either an increase or a decrease) will be made by the SRC and the Investigator based on safety and tolerability observed in at the patients at the prior dose level, with the dosing decisions indicated in the TITE-BOIN design.

The dosing schedule may also be adjusted to expand a dosing cohort to further evaluate safety and tolerability findings at a given dose level. The study procedures for these additional patient(s)/cohort(s) will be the same as that described for other study patients/cohorts.

If moderate or severe AEs are consistently observed across patients in a cohort or if unacceptable toxicity, reasonably attributable to LC or the combination of LC and TMZ in the opinion of the Investigator are observed, dose escalation may be temporarily halted and no further patients will be dosed until a full safety review of the study by the SRC has taken place. Relevant reporting and discussion with the Medical Monitor, relevant personnel, and the Institutional Review Board (IRB)/Independent Ethics Committee (IEC) will take place before resumption of dosing.

If the same SAE occurs in more than 2 patients in a cohort, dose escalation will be temporarily halted and no further patients will be dosed until a full safety review of the data has taken place. Relevant reporting and discussion with the Medical Monitor, relevant personnel, and the IRB/IEC will take place before resumption of dosing.

6 DISCONTINUATION OF STUDY INTERVENTION AND PATIENT DISCONTINUATION/WITHDRAWAL

6.1 Discontinuation of Study Intervention

Patients who discontinue treatment with LC will continue to be followed for AEs for an additional 30 days after the last dose of LC and the last dose of TMZ, and then for progression-free survival and overall survival as described in [Section 4.1.6](#).

See the Schedule of Assessments (SoA) for data to be collected at the time of discontinuation of study intervention.

Discontinuation of study intervention for abnormal liver function should be considered by the Investigator when a patient meets one of the conditions outlined in the eligibility criteria of if the Investigator believes that it is in best interest of the patient.

If a clinically significant finding is identified (including, but not limited to changes from baseline in QTc interval after enrollment (using the Bazett formula [QTcB]), the Investigator or qualified designee will determine if the patient can continue in the study and if any change in patient management is needed. This review of the ECG printed at the time of collection must be documented. Any new clinically relevant finding should be reported as an AE. Males with QTcB interval > 450 msec and females with QTcB interval > 460 msec should discontinue treatment with LC. Any patient with an increase from baseline in the QTcB interval > 15 msec should discontinue LC.

See the SoA for data to be collected at the time of intervention discontinuation and follow-up and for any further evaluations that need to be completed.

6.1.1 Temporary Discontinuation of Radiation

Administration of LC will continue through a temporary discontinuation of radiation.

6.1.2 Rechallenge

A patient who develops a DLT or AE attributed to LC that requires discontinuation of LC will not be rechallenged with LC.

6.2 Patient Discontinuation/Withdrawal from Study

- A patient may withdraw from the study at any time at their own request, or may be withdrawn at any time at the discretion of the Investigator for safety, behavioral, compliance, or administrative reasons.
- At the time of discontinuing from the study, if possible, an End of Treatment visit should be conducted, as shown in the SoA. The SoA indicates what data is to be collected at the time of study discontinuation and follow-up and any further evaluations that need to be completed. The patient will be permanently discontinued both from the study intervention and from the study at that time.

- If the patient withdraws consent for disclosure of future information, the Sponsor may retain and continue to use any data collected before such a withdrawal of consent.
- If a patient withdraws from the study, they may request destruction of any samples taken and not tested, and the investigator must document this in the site study records.

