4.1.6 Safety Monitoring

- The study will be overseen by an SRC composed of the Medical Monitor and 2 voting members from the Sidney Kimmel Comprehensive Cancer Center at Johns Hopkins. The SRC will convene to review data and discuss next steps at the end of every dose level (once all patients complete the 10-week evaluation period), the data have been cleaned, and the DLT outcomes are determined. In addition, the SRC will meet every 6 months at minimum, and as needed to review AEs. The Principal Investigator and study biostatistician will attend SRC meetings. The SRC will sign off on each dose level before activation of a new dose cohort or expansion of a dose cohort may begin.
- All women of childbearing potential (WOCBP) should be instructed to contact the Investigator immediately if they suspect they might be pregnant (eg, missed or late menstrual period) at any time during study participation. The Investigator must immediately notify the Medical Monitor in the event of a confirmed pregnancy in a patient participating in the study.
- The reason(s) for protocol therapy discontinuation, the reason(s) for study removal, and the corresponding dates must be documented in the Case Report Form (CRF).

- Adverse events will be followed for 30 days after the last dose of LC. Patients removed from the study for unacceptable AEs will be followed until resolution or stabilization of the AE.

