6.3 Lost to Follow-up

A patient will be considered lost to follow-up if they repeatedly fail to return for scheduled visits and is unable to be contacted by the study site.

The following actions must be taken if a patient fails to return to the clinic for a required study visit:

- The site must attempt to contact the patient and reschedule the missed visit as soon as possible and counsel the patient on the importance of maintaining the assigned visit schedule and ascertain whether or not the patient wishes to and/or should continue in the study.
- Before a patient is deemed lost to follow-up, the Investigator or designee must make every effort to regain contact with the patient (where possible, 3 telephone calls and, if necessary, a certified letter to the patient's last known mailing address or local equivalent methods). These contact attempts should be documented in the patient's medical record.
- Should the patient continue to be unreachable, they will be considered to have withdrawn from the study.

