7.3.4 Use of Criteria from Response Assessment in Neuro-Oncology for Assessment of Progression

Progressive disease is defined by *any* of the following:

- a) $\geq 25\%$ increase in sum of the products of perpendicular diameters of enhancing lesions compared to the smallest tumor measurement obtained either at baseline

- (if no decrease) or best response, on stable or increasing doses of corticosteroids. (Stable doses of corticosteroids include patients not on corticosteroids.)
- b) Significant increase in T2-fluid-attenuated inversion recovery (FLAIR) nonenhancing lesion on stable or increasing doses of corticosteroids compared to baseline scan or best response following initiation of therapy, not due to comorbid events (RT, demyelination, ischemic injury, infection, seizures, postoperative changes, or other treatment effects)
 - c) Any new lesion
 - d) Clear clinical deterioration not attributable to other causes apart from the tumor (eg, seizures, medication adverse effects, complications of therapy, cerebrovascular events, infection, etc) or changes in corticosteroid dose. A diagnosis of clinical progression or deterioration may be made at the discretion of the treating physician.
 - e) Failure to return for evaluation due to death or deteriorating condition
 - f) Clear progression of nonmeasurable disease

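### Section 6.2 takes patients withdrawn by the Investigator off the study as well as off treatment, while 6.1 and the Schedule of Activities keep following patients stopped for the same reasons; no rule says which applies, so OS and PFS risk informative censoring

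*Protocol*

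**What the plan says.** Protocol 6.2 covers withdrawal from the study. Besides leaving at their own request, a patient "may be withdrawn at any time at the discretion of the Investigator for safety, behavioral, compliance, or administrative reasons". After an End of Treatment visit, if one is possible, 6.2 adds: "The SoA indicates what data is to be collected at the time of study discontinuation and follow-up". The last sentence of the same bullet is: "The patient will be permanently discontinued both from the study intervention and from the study at that time". Withdrawal of consent has its own bullet: "If the patient withdraws consent for disclosure of future information, the Sponsor may retain and continue to use any data collected before" that withdrawal.

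Other sections describe continued follow-up:

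- **6.1** follows patients who stop LC for adverse events for 30 days after the last doses of LC and temozolomide, "and then for progression-free survival and overall survival as described in" Section 4.1.6.
- **4.1.6**, with the same rule in Schedule of Activities note 12 and in 7.2.2, says: "Patients removed from the study for unacceptable AEs will be followed until resolution or stabilization of the AE".
- **Schedule of Activities note 13, 4.1.5, 7.3.5 and 7.3.6** follow patients for survival, progression or both every 2 months for 2 years after the last LC dose, then every 6 months. Telephone, clinic visit and medical records are all accepted sources.
- **4.1.2** lists unacceptable adverse events, noncompliance and changes in the patient's condition among the reasons for ending treatment.

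For patients who cannot be contacted, 6.3 says: "Should the patient continue to be unreachable, they will be considered to have withdrawn from the study". Section 8.4.7 censors OS at the last date known alive and PFS at the last tumor assessment.

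**The concern.** Stopping treatment and leaving the study are different events, and the protocol does not keep them apart. The Investigator's grounds for withdrawal in 6.2 (safety, compliance) overlap the grounds for ending treatment in 4.1.2 (unacceptable adverse events, noncompliance). Two sites, or one site on two occasions, could handle identical patients differently. One patient would supply survival and progression data for years, and the other would supply none after the withdrawal date.

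This matters because Kaplan-Meier estimates are unbiased only if censoring is unrelated to prognosis. Patients withdrawn for safety or compliance in high-grade glioma may well have a worse outlook than those who stay. OS and PFS are reported at each dose level. Escalation enrolment stops once one level has 12 patients, and a level used for expansion gains at most 6 more, so it holds about 18. A few lost patients carry weight in groups of that size. Vital status that sites have stopped collecting cannot be restored at the analysis stage.

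**Working it through.** **1. Sections side by side for one patient.** Take a patient who stops LC for toxicity or noncompliance and has not withdrawn consent.

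| Question | 6.1, 4.1.5, 7.3.5–7.3.6, note 13 | 6.2 |
|---|---|---|
| Treatment ends? | Yes | Yes |
| Study participation ends? | No | Yes, at that time |
| PFS and OS status collected later? | Yes, including from records | Points to the Schedule of Activities for follow-up, then ends participation |
| Outcome under 8.4.7 | Event, or censored at latest contact | Censored near withdrawal |

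No sentence says when stopping treatment becomes withdrawal from the study. The pointer to the Schedule of Activities in 6.2 does not settle this, because the sentence after it ends participation.

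**2. Adverse events.** Section 4.1.6, note 12 and 7.2.2 expressly follow patients removed from the study for unacceptable adverse events, and 7.2.4 follows serious events to resolution, stabilization, another explanation or loss to follow-up. The gap therefore concerns PFS and OS.

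**3. Cross-reference.** Section 6.1 sends the reader to 4.1.6 for PFS and OS follow-up. Section 4.1.6 contains adverse-event follow-up only; the survival and progression schedule is in 4.1.5.

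**4. Possible size.** The protocol states no withdrawal rate and no bias figure, so there is nothing of its own to reproduce. For scale:

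- From the protocol: median OS 14.6 months with radiotherapy plus temozolomide (1.1), and up to 34 weeks of treatment (1.1).
- Assumed: exponential survival; a share *f* of patients given a withdrawal time uniform over the 34 weeks and censored there if still alive; hazard multiplied by *k* after withdrawal.

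Hazard: λ = ln 2 / 14.6 = 0.04748 per month. Treatment period: T = 34 × 7 / 30.4375 = 7.82 months.

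In large samples, Kaplan-Meier with withdrawn patients censored estimates exp(−12λ) = 0.566 at 12 months, with a median of 14.6 months, whatever *f* and *k* are.

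True 12-month OS = (1 − f) · exp(−12λ) + f · exp(−12kλ) · [exp((k−1)λT) − 1] / [(k−1)λT].

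- k = 1.5: second factor 0.4255 × 1.0988 = 0.4675
- k = 2: 0.3200 × 1.2109 = 0.3875
- k = 3: 0.1810 × 1.4830 = 0.2685

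Smallest case, f = 10%, k = 1.5: 0.9 × 0.5657 + 0.1 × 0.4675 = 0.556, an overstatement of 0.010.

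Largest case, f = 30%, k = 3: 0.7 × 0.5657 + 0.3 × 0.2685 = 0.477, an overstatement of 0.089.

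| Overstatement of 12-month OS (points) | k = 1.5 | k = 2 | k = 3 |
|---|---|---|---|
| f = 10% | 1.0 | 1.8 | 3.0 |
| f = 20% | 2.0 | 3.6 | 5.9 |
| f = 30% | 3.0 | 5.3 | 8.9 |

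A simulation of 500,000 patients gave the same values to within sampling error. Some marked patients die before their withdrawal time, so the shares actually censored were about 8%, 17% and 25%. The true median ran from 14.1 months (f = 10%, k = 1.5) to 11.3 months (f = 30%, k = 3), against a Kaplan-Meier reading of 14.6. With k = 1 there is no bias.

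**The case against.** The best defence is that 6.1 and 6.2 govern different acts. A patient who stops LC for toxicity falls under 6.1 unless the Investigator also withdraws them from the study, and nothing suggests this second step would be common. Section 6.2 also refers to the Schedule of Activities, where notes 12 and 13 carry the follow-up. The list in 4.1.2 nowhere says its reasons end treatment alone; it even includes the patient's own decision to leave the study. OS and PFS are secondary and descriptive, with no hypothesis test (8.1), and no dose decision or sample size depends on them.

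Most of this limits the consequence and leaves the ambiguity in place. The grounds overlap, 6.2 requires no withdrawal of consent, and its final sentence overrides the pointer before it. The secondary, descriptive status of the endpoints stands in full, as does the point that the number of patients affected is unknown.

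Three stronger readings are tempting but not supported:

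- **Open adverse events go unfollowed after withdrawal.** The rules in 4.1.6, note 12, 7.2.2 and 7.2.4 say otherwise.
- **Section 6.3 contradicts the progression criterion in 7.3.4(e)**, "Failure to return for evaluation due to death or deteriorating condition". That criterion needs a known cause; 6.3 concerns patients who cannot be reached. A known deterioration remains a PFS event, since 8.4.7 censors only patients without evidence of progression. No section expressly keeps following unreachable patients, and 7.2.4 agrees with 6.3. What remains is narrower: survival status may be taken from medical records, which needs no contact, and 6.3 does not say whether that source stays open.
- **OS and PFS are in fact biased.** The documents support only a conditional risk.

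**Conclusion.** The point holds as an unresolved conflict over who is followed. For a patient stopped for toxicity or noncompliance who has not withdrawn consent, the protocol supports both continued PFS and OS follow-up and complete exit from the study, with no rule for choosing. Where 6.2 is applied, the patient is censored under 8.4.7.

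The estimates would be optimistic if withdrawn patients do worse than those who remain. Under the assumed shares and hazard ratios above, 12-month OS is overstated by about 1 to 9 points. That range rests wholly on *f* and *k*, on exponential survival and on uniform withdrawal times. It is a large-sample bias for OS and does not describe sampling error in groups of 18 or fewer. No figure is offered for PFS, where 7.3.4(e) turns some losses into events. The primary endpoint and the escalation rules are outside this point.

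**What to change.** Amend three places:

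1. **6.2.** Limit permanent discontinuation from the study to patients who withdraw consent to follow-up. State that withdrawal initiated by the Investigator ends study treatment only, and that follow-up under 6.1 and Schedule of Activities notes 12 and 13 (adverse events, PFS and OS, including from medical records) continues.
2. **6.3.** State that survival status of unreachable patients who have not withdrawn consent may still be obtained from medical records, a source that 4.1.5 and 7.3.5 already accept.
3. **6.1.** Change the cross-reference for PFS and OS follow-up from 4.1.6 to 4.1.5.

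The cost is a wording amendment and a few additional contacts or record checks within a follow-up scheme already planned. The change belongs in the protocol because it determines which data sites collect.
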